**8.4 Additional Analyses**

[REDACTED]

**8.5 Safety Endpoints**

AEs will be reported by number, severity, timing, and relationship to the study procedures (imaging modality, colonoscopy), as described in Sections 11.7 and 11.8. The recording of adverse events for all

enrolled subjects will begin with the start of the CCE/CTC bowel preparation and end with the OC Follow-up call. All AEs will be captured, regardless of severity or relationship to the procedure.

## **8.6 Qualifications and Training**

### **8.6.1 Site Principal Investigator (Gastroenterologist)**

A gastroenterologist at each site, either performing the capsule or colonoscopy procedure, will be designated as the Site Principal Investigator for that site. There will be only one Principal Investigator for each site. All subject consent and randomization will be conducted by the Site Principal Investigator (gastroenterologist).

Board-certified gastroenterologists in accordance with medical and hospital guidelines will be considered for participation as site investigators in this study. Physicians in training (residents, fellows) and physician assistants may assist the Study Investigator in any aspect of the procedure as per standard procedures and practices at his/her institution and provided that they are experienced with the use of the PillCam® CCE system. CCE Local readers will be trained on capsule reading in accordance with the e-learning program and will be required to complete this training session with a score above 80%.

Each Investigator participating in the clinical trial and the associated clinical study staff will receive training on the clinical protocol. This includes training on AE reporting, case report form (CRF) completion, and Good Clinical Practice (GCP), as well as the device and system (including procedural use, device characteristics, shelf life and storage requirements, warnings, precautions, and contraindications).

### **8.6.2 CCE Central Reader Qualifications**

Central readers will be experienced gastroenterologists trained to read PillCam® COLON 2 RAPID® videos. The central readers are independent physicians and are not site investigators.

Experience and training are required in order to accurately interpret capsule endoscopy videos. The central readers will be trained by the sponsor on reading PillCam® COLON 2 RAPID® videos. The training will include RAPID® 8.3 software and RAPID® videos evaluation training.

### **8.6.3 Radiologists**

Radiologists associated with each site will collaborate with the site principal investigator (gastroenterologist) to conduct the CTC examination. The radiologist can be assigned from a remote site. Experience and training are required in order to accurately perform CTC examinations, as defined in the ACR-SAR-SCBT-MR Practice Parameter for the Performance of Computed Tomography Colonography in Adults, Section III, Qualifications and Responsibilities of Personnel (23). In accordance with the practice parameters, radiologists meeting the qualifications will have, “substantial knowledge of radiation biology, the physics of CT scanning, the principles of CT image acquisition and postprocessing, including the use of diagnostic workstations, and the design of CT protocols, including rate and timing of contrast administration. The physician also will have substantial experience in CT interpretation, including CT of extracolonic structures that will be included on the CTC examination.” Education regarding patient preparation, bowel insufflation, and CT image acquisition as well as formal hands-on training are also required in accordance with the practice parameters, including “the interpretation, reporting, and/or supervised review of at least 50 endoscopically confirmed CTC cases.” The CTC exam sites will also be

expected to possess expertise in patient preparation, bowel insufflation, and CT image acquisition. Refer to the ACR-SAR-SCBT-MR Practice Parameters for additional details (23).

ACR-SAR-SCBT-MR Practice Parameter certification is required prior to reading CTC study cases.

Each radiologist participating in the clinical trial and the associated clinical study staff will receive training on the clinical protocol.

#### **8.6.4 CTC Central Reader Qualifications**

CTC central readers will be expected to possess the following expertise, in accordance with the ACR-SAR-SCBT-MR Practice Parameter for the Performance of Computed Tomography Colonography in Adults, Section III, Qualifications and Responsibilities of Personnel (23). ACR-SAR-SCBT-MR Practice Parameter certification is required prior to reading CTC study cases.

1. Formal hands-on interactive training using dedicated CTC software, including the interpretation, reporting, and/or supervised review of at least 50 endoscopically confirmed CTC cases using primary 2D and/or primary 3D search with application of routine problem-solving techniques. Ideally this collection of training cases will be chosen to demonstrate the gamut of appearances of colonic polyps and cancer and CTC interpretation pitfalls. Additionally, the cases should include examinations performed for a variety of indications (e.g., screening, symptomatic, incomplete colonoscopy with subsequent validation) and acquisition techniques (e.g., with and without fluid tagging and intravenous contrast).
2. A total of 50 cases every 2 years should be reviewed to maintain skills in CTC.

In addition to the above criteria, central readers will be required to have interpreted at least 500 prior CTC studies.

#### **8.7 Subject Selection and Enrollment**

After being informed of the nature of the study, the subject will sign a written informed consent form (ICF) that has been approved by the appropriate IRB of the respective clinical site. Enrollment of up to 320 subjects is planned. Interim analyses will be performed every 80 subjects (40 per arm) to reassess sample size based on a Bayesian adaptive design.

Subjects' participation in the study will last approximately 5–6 weeks, including bowel preparation, CCE or CTC, both blinded and unblinded OC procedures, and follow-up 5-9 days post-OC procedure via telephone.

Subjects who meet all inclusion criteria, but no exclusion criteria, will be eligible for participation in the study.

##### **8.7.1 Inclusion Criteria**

1. Subject is between 50 and 75 years of age (for African Americans only, subject is between 45-75 years of age).
2. Subject is classified as average risk per the American Gastroenterological Association Guidelines on Colorectal Cancer Screening: Individuals without inflammatory bowel disease, or high-risk genetic syndromes or personal history of CRC or adenomas or family history of either CRC or

adenomas in a first degree relative before age 60 years. Subjects with 2 second degree relative affected with colorectal cancer are also considered average risk.

3. Subject is willing and able to participate in the study procedures and to understand and sign the informed consent.

#### 8.7.2 Exclusion Criteria

1. Subject with history of colorectal cancer or adenoma (including those identified by computed tomography [CT], optical colonoscopy, sigmoidoscopy, etc.).
2. Subject with history of negative colonoscopy within 10 years, as these subjects would be defined as not requiring screening in this timeframe. For subjects with alternative screening methods, refer to applicable guidelines.
3. Subject with currently suspected or diagnosed with hematochezia, melena, iron deficiency with or without anemia, or any other rectal bleeding, including positive fecal occult blood test of any variety.
4. Subject with any current condition believed to have an increased risk of capsule retention such as suspected or known bowel obstruction, stricture, or fistula.
5. Subject with current dysphagia or any swallowing disorder.
6. Subject with current serious medical conditions that would increase the risk associated with CCE, CTC, or colonoscopy that are so severe that screening would have no benefit.
7. Subject with a cardiac pacemaker or other implanted electromedical device.
8. Subject expected to undergo MRI examination within 7 days after ingestion of the capsule.
9. Subject with clinical evidence of renal disease within the past 6 months, defined as estimated glomerular filtration rate (GFR) outside of the normal reference range.
10. Subject with current known gastrointestinal motility disorders.
11. Subject with allergies or known contraindication to the medications or preparation agents used in the procedure as described in the relevant instructions for use.
12. Subject has an estimated life expectancy of less than 6 months.
13. Subject is considered to be part of a vulnerable population (e.g. prisoners or those without sufficient mental capacity).
14. Subject is pregnant, suspected pregnant, or is actively breast-feeding. Females of child-bearing potential will be required to provide either a urine pregnancy test or serum pregnancy test as part of the participant's standard of care regardless of their participation in the study (except for subjects who are surgically sterile or are post-menopausal for at least two years).
15. Subject has participated in an investigational drug or device research study within 30 days of enrollment that may interfere with the subject's safety or ability to participate in this study.

#### 8.8 Withdrawal of Subjects

Subjects may withdraw from the study at their own request or at the request of their legally acceptable representative. The investigator may withdraw a subject from the study at any time for the following reasons:

- Severe side effects clearly related to the study procedures
- Presence or appearance of exclusion criteria
- Appearance of accompanying diseases rendering further participation in the study impossible
- A significant protocol violation, as determined either by the sponsor or the investigator
- Subject noncompliant with investigational procedures
- Subject noncompliant with visits
- At the specific reasonable request of the study sponsor

The sponsor must be informed of each withdrawal case. The reason for withdrawal must be recorded in the CRF and in the subject file.

### **8.9 Procedures to Minimize Bias**

A 1:1 randomization will be employed to minimize bias relative to the comparison of the two study arms. In addition, RAPID® videos and CTC images will be randomly distributed among the central readers.

In addition, the confirmatory OC will be conducted first blinded to the CCE/CTC results and then unblinded.

[figure not shown]
### **8.10 Study Procedures**

#### **8.10.1 Study Flow**

Study procedures are depicted in the figure below. Subjects will undergo a blood test for renal function and will then be 1:1 randomly assigned to undergo either CCE or CTC. Subjects with eGFR < 45 may be discontinued from the study upon physician discretion, since eGFR value < 45 will be problematic for the CTC procedure, but not for the CCE procedure.

All subjects will undergo a confirmatory OC procedure within 5 weeks of the CCE or CTC procedure. The confirmatory OC will be conducted first blinded to the CCE/CTC results and then unblinded, if there are discrepancies in results, as shown below.

**Figure 1.** Study Flow Chart

### 8.10.2 Screening and Informed Consent

A screening/baseline visit will be performed within 30 days prior to the scheduled CCE or CTC procedure to assess preoperative eligibility. In the event that the screening and eligibility assessment takes place more than 30 days prior to the planned randomized procedure (CCE or CTC) date, the investigator should contact the subject prior to the procedure date to assure there is no change in the subject's medical condition. All potential subjects who meet all of the inclusion criteria, but none of the exclusion criteria, will be invited to participate in the study.

At the screening visit, subjects will be approached to obtain written informed consent prior to any study specific procedures being performed. The purpose of the study and the benefits and risks of the procedures will be explained to the subject and the consent process must be documented accordingly in the medical record. Subjects who agree to study participation must sign an IRB-approved ICF. Subjects will be informed that their participation in this study is voluntary and they may refuse to participate or discontinue from the study at any time. Subjects will be given the opportunity to ask the investigator questions so that they are adequately informed about the research. A copy of the signed informed consent must be provided to the subject and the informed consent process will be documented in source documents.

If new information becomes available that may affect a subject's decision to continue to take part in the study, this information will be discussed with the subject by the investigator.

Once eligibility is confirmed and informed consent has been signed, the subject's baseline condition will be assessed to include: renal function assessment, date of birth, gender, height, weight, waist circumference, cigarette smoking history and prior abdominal surgery.

- Relevant medical history will be assessed based on clinical condition categorized by category codes specified in the case report form.
- Documentation will occur of previous GI procedures, such as OC and CTC, including number, date, and results from the last procedure.
- Female subjects will be assessed for childbearing potential, and if they do have childbearing potential, they will undergo a urine pregnancy test. If the test is positive, they will be withdrawn from the study. If the pregnancy test is negative, these subjects should practice contraceptive methods through the course of the study. Additional urine pregnancy test will be performed during visit 2, prior to capsule ingestion or CTC.
- All subjects will be tested for renal function using a blood test (eGFR)

#### **8.10.3 Randomization**

Subjects will be randomized in a 1:1 ratio to receive screening by either CCE (using the PillCam® endoscopy system with PillCam® COLON 2 capsule) or CTC. The study will utilize randomization in blocks in order to allocate subjects into two arms:

- Group 1: CCE
- Group 2: CTC

Randomization will occur at the screening visit at the gastroenterology site, after eligibility has been confirmed and signed informed consent has been obtained. Due to the nature of the test and control screening procedures, neither the subject nor the investigator will be blinded to the assigned study arm.

#### **8.10.4 Screen Failures**

A subject is considered enrolled in the study when the ICF is signed. Only subjects who received study-assigned procedures will be followed. Any subject who is determined to be ineligible for study participation prior to undergoing the randomized (CCE or CTC) procedure, will be considered a screen failure. The reason for the screen failure will be clearly captured on the applicable CRFs.

#### **8.10.5 Randomized Procedure (CCE or CTC)**

Detailed procedures for the bowel preparation and conduct of the randomized CCE or CTC procedures are included in Appendix A (CCE procedure instructions) and Appendix B (CTC procedure instructions).

Subjects will be instructed to follow a detailed colon preparation regimen prior to and during the randomized CCE or CTC procedure. With the exception of Gastrografin, all colon preparation products will be standard colon cleansing products approved by the FDA and are detailed in Appendices A and B.

### 8.11 Image Reading

All CCE RAPID® videos and CTC images will be evaluated by local and central readers. For CCE studies at the local site, there will be one individual performing colonoscopy and another reading the video. For CCE studies and CTC images, local readers will perform the evaluation at the same time frame as reading performed by central readers.

All study analyses will be based the results of two sets of central readers, one set for reading of the CCE RAPID® videos and one set for reading the CTC images. All readers must read each video or image independently without input from other readers, investigators, or other site staff. Each reader will produce an independent report for each video or image. Videos/images will be randomly distributed among the readers.

All study analyses will be based on the results of the central readers and the findings of the central readers are final.

Readers will provide a report of their findings to the sponsor within 2 weeks of capsule ingestion or the CTC procedure in order to allow subjects to return within 5 weeks of capsule ingestion or the CTC procedure to undergo the OC procedure.

Detailed reader instructions are included in Appendix A4 (CCE reader instructions) and Appendix B4 (CTC reader instructions).

#### 8.11.1 OC Procedure

All subjects will undergo a confirmatory OC procedure within 5 weeks of the randomized CCE or CTC procedure. The confirmatory OC will be conducted once or twice, depending on findings compared to CCE or CTC, if discrepancies between results exist. For the first (blinded) OC procedure, the operator must be blinded to both the central reader results and any local reader reports of the randomized CCE/CTC results. After the blinded OC procedure, the operator will read the central reader results for CCE/CTC. If CCE/CTC results are not congruent to the blinded OC procedure results, an unblinded OC procedure will be performed to verify polyp presence. Instructions for the bowel preparation and conduct of the OC procedure are provided in Appendix C.

Diagnostic yield of CCE/CTC will be calculated in relation to the confirmatory OC results. See Appendix D for details on polyp-matching algorithm.

#### 8.11.2 Study Assessments Table

Table 2. Study Schedule

	Screening (Visit 1; -30 days)	CCE or CTC Procedure (Visit 2; Day 0)	Follow-Up via Telephone (5 – 9 days after Visit 2)	OC-Blinded, then OC- Unblinded (Visit 3) (Within 5 weeks of Visit 2)	Follow-Up via Telephone (5 – 9 days after Visit 3)
Informed consent	X				
Preoperative eligibility criteria	X				

Table 2. Study Schedule

	Screening (Visit 1; -30 days)	CCE or CTC Procedure (Visit 2; Day 0)	Follow-Up via Telephone (5 – 9 days after Visit 2)	OC-Blinded, then OC- Unblinded (Visit 3) (Within 5 weeks of Visit 2)	Follow-Up via Telephone (5 – 9 days after Visit 3)
Demographics	X				
Medical/surgical history	X				
Height and weight	X				
Pregnancy test a	X	X			
Randomization	X				
Blood test for renal function (GFR)	X				
Effectiveness endpoints		X		X	
Adverse events		X	X	X	X
Subject procedure preference					X
Study exit					X

a. Pregnancy test to be administered to females of reproductive age who have not undergone previous sterilization or hysterectomy procedures. If the test is positive, they will be withdrawn from the study. If the pregnancy test is negative, these subjects should practice contraceptive methods through the course of the study. Additional urine pregnancy test will be performed during Visit 2, prior to capsule ingestion or CTC.

## 9.0 Statistical Analysis

### 9.1 Sample Size Determination

The sample size is estimated based on the primary non-inferiority hypothesis under a Bayesian adaptive design. Interim assessments will be performed at every 80 subjects (40 per arm) with a maximum of 320 subjects (160 per arm). Early success will be claimed if the pre-defined success criterion is met.

The following parameter assumptions are used in the estimation, based on prior literature (15).

- Predicted CCE diagnostic yield: 25%
- Predicted CTC diagnostic yield: 15%
- Noninferiority hypothesis with a 5% margin
- Accounting for approximately 10% attrition

With the assumptions, a total of 320 subjects (160 per arm) with interim assessments at every 80 subjects (40 per arm) will provide more than 80% power to test the primary hypothesis at the significance level of 5%.

Note that the expected sample size will be smaller than 320 with the adaptive Bayesian design since an early interim claim for success is possible. Additionally, if non-inferiority is proven, superiority will also be tested (which is not statistically powered at 80%).

### 9.2 Primary Hypothesis Analysis

The primary statistical hypothesis is that the diagnostic yield (proportion of subjects having an actionable lesion, defined as any polyp or mass lesion  $\geq 6$  mm) will be noninferior for CCE compared to CTC in a screening population, that is,  $H_0: p_1 \leq p_0 - \delta$  versus  $H_a: p_1 > p_0 - \delta$  where  $p_1$  and  $p_0$  are the diagnostic yield rates for CCE and CTC respectively. The non-inferiority margin ( $\delta$ ) is pre-defined to be 5%.

The probability of  $(p_0 - p_1 < \delta)$  will be computed from the posterior distribution of the difference  $(p_0 - p_1)$ . Should the posterior probability  $\Pr(p_0 - p_1 < \delta | Data)$  be at least 98% at the interim or 96% at the final analysis, then the null non-inferiority hypothesis will be rejected, and non-inferiority of CCE to CTC will be claimed. The probabilities of 98% (interim) and 96% (final) are chosen to ensure the false positive rate (type I-like error) is well controlled.

If the non-inferiority of CCE to CTC is established with respect to the diagnostic yield, a superiority test will also be performed. The null superiority hypothesis is  $H_0: p_1 \leq p_0$ , and the alternative superiority hypothesis is  $H_a: p_1 > p_0$ . The probability of  $(p_1 > p_0)$  will be computed from the posterior distribution of the difference  $(p_1 - p_0)$ . If the posterior probability  $\Pr(p_1 > p_0 | Data)$  is at least 98% (interim) or 96% (final), then the null superiority hypothesis will be rejected and superiority of CCE to CTC will be claimed.

If the interim non-inferiority analysis does not meet the pre-defined success criteria, there will be no early claim for success and the study will continue until completion.

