#### 9.6 Interim Analyses

Interim analyses are planned after each 80 subjects (40 per arm) have completed the primary endpoint, until 320 total subjects or the non-inferiority for the primary endpoint is met (whichever occurs first).

Additionally, sample size re-assessments will be carried out during interim analyses. The conditional power will be calculated to determine if a sample size adjustment is necessary. There will not be necessary to adjust the alpha level if the conditional power is greater than 50% (i.e., within the promising zone). If the chance of success is too low (i.e. <10%), *early stopping for futility may be considered*.

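### With three interim looks and a final, the 98%/96% posterior thresholds give a false-positive rate of about 6.5–7.5% under flat priors, not the stated 5%

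*Combined protocol and SAP*

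**What the plan says.** Section 9.1 gives the planning assumptions: CCE yield 25%, CTC yield 15%, a 5-point margin and about 10% attrition. It says that 320 subjects with looks every 80 "will provide more than 80% power to test the primary hypothesis at the significance level of 5" per cent. On stopping, it adds: "Early success will be claimed if the pre-defined success criterion is met".

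Section 9.6 repeats the schedule: "Interim analyses are planned after each 80 subjects (40 per arm) have completed the primary endpoint". Looks continue until 320 subjects or until non-inferiority is met. The synopsis (section 4.0) and section 8.7 agree. The plan therefore has success looks at 80, 160 and 240 subjects and a final at 320.

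Section 9.2 sets the rule. Should the posterior probability that CTC exceeds CCE by less than 5 points "be at least 98% at the interim or 96% at the final analysis, then the null non-inferiority hypothesis will be rejected". The thresholds are justified in one sentence: "The probabilities of 98% (interim) and 96% (final) are chosen to ensure the false positive rate (type I-like error) is well controlled". No prior, simulation or achieved error rate is given. The same thresholds are reused for superiority.

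On futility, section 9.6 says only that stopping may be considered when the chance of success is below 10%.

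**The concern.** Under a flat prior, a 98% posterior threshold behaves much like a one-sided 2% test and a 96% threshold like a one-sided 4% test. A single final test at 96% would already use about 4% of the stated 5%, which leaves about 1 point for the interims. Three interims at 2% each, even allowing for the correlation between looks, use far more than that. The 5% level and the reassurance about false positives would then both be wrong for the trial's primary claim, and a reader would take a non-inferiority result as better protected against error than it is.

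**Working it through.** **Inputs**

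- Thresholds: 0.98 at each interim, 0.96 at the final (9.2).
- Looks: 40, 80, 120 and 160 per arm (9.1, 9.6), with 1:1 allocation (8.10.3).
- Margin: 0.05. Type I error is evaluated at the boundary p1 = p0 − 0.05, where p1 is the CCE yield and p0 the CTC yield.
- Prior: not stated. Assumed Beta(1,1) in each arm, with Jeffreys Beta(0.5,0.5) as the alternative.
- Futility: not credited, because it is optional.

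**Method**

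For every pair of counts at each look, compute Pr(p0 − p1 < 0.05 | data) from the two beta posteriors. Carry the joint binomial distribution of the counts forward from look to look, removing the outcomes that have already met the threshold. The probability removed, summed over the four looks, is the rejection probability.

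**The plan's power figure**

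At 25% versus 15% with uniform priors, power is 95.6% with 160 per arm and 93.7% with 144 per arm (10% attrition). The statement of more than 80% holds.

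**The plan's 5% figure: normal approximation**

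The critical values are Φ⁻¹(0.98) = 2.054 for three looks and Φ⁻¹(0.96) = 1.751 for the last. The correlation between looks i < j is √(n_i/n_j), so

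type I error = 1 − Pr(Z1 < 2.054, Z2 < 2.054, Z3 < 2.054, Z4 < 1.751) = 6.52%.

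With the same thresholds and fewer looks:

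| Looks | Type I error |
|---|---|
| Final only | 4.00% |
| One interim at 160 subjects, then final | 5.05% |
| One interim at 80 subjects, then final | 5.46% |
| Three interims, then final (as planned) | 6.52% |

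**Exact results, planned four looks, CTC yield 10–50%**

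| Prior | 40/80/120/160 per arm | 36/72/108/144 per arm |
|---|---|---|
| Beta(1,1) | 6.55–6.81% | 6.56–7.06% |
| Beta(0.5,0.5) | 6.66–7.48% | 6.65–7.86% |

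At the planning CTC yield of 15% and 160 per arm, the values are 6.79% (uniform) and 6.98% (Jeffreys). The three interims alone use about 4.4–4.8%, or up to 5.3% with Jeffreys priors at a 10% yield. Relative to 5%, the 160-per-arm range is 6.55/5 = 1.31 to 7.48/5 = 1.50.

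**Where the 5% may come from**

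With one interim at 160 subjects and a uniform prior, the exact rate is 5.1–5.4%. That is near the stated level, but it is not the schedule in 9.1 and 9.6. This origin is an inference, and the excess does not depend on it.

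**The case against.** **The prior.** This is the strongest objection. The rate depends on a prior that the plan does not state, and a more informative one lowers it. Over CTC yields of 10–30%, Beta(2,2) in each arm gives 5.2–6.4%. Beta(5,5) gives 3.2–5.8%, with 4.5% at a 15% yield. So 6.5–7.5% is conditional on flat priors, and that stands. It does not rescue the plan: even Beta(5,5) fails to hold 5% at every yield, and a prior chosen for that purpose would have to be pre-specified.

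**The number of looks.** Section 9.2 refers to the interim in the singular and says that, after a miss, the study runs to completion, which suggests one interim. The wording is loose and should be corrected. Sections 9.1 and 9.6 are explicit that looks occur every 80 subjects with early success allowed.

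**Futility.** If the 10% rule were binding, the rate would be about 5.3–5.8% (conditional power at the observed trend), 5.9–6.3% (predictive probability) or 6.5–6.8% (conditional power at the design rates). All exceed 5%, and the rule is optional.

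**A Bayesian design need not control type I error.** This plan says that it does: 9.1 gives a significance level and 9.2 justifies the thresholds by false-positive control. The alpha remark in 9.6 concerns sample-size adjustment, not repeated success looks.

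**Sidedness.** If the 5% were two-sided, the intended one-sided rate would be 2.5% and the excess 2.6–3 times. The hypothesis is one-directional and a 96% final threshold does not fit a 2.5% intention, so nothing here rests on that reading.

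**Conclusion.** The concern holds. On the documented schedule, the thresholds in 9.2 do not deliver the 5% level in 9.1. Under either usual flat prior the type I error is about 6.5–7.5% with 160 per arm, and up to 7.9% with 10% attrition, Jeffreys priors and a 10% CTC yield. No flat-prior case examined reaches 5%. The result assumes four looks, non-binding futility and no sample-size increase under the re-assessment in 9.6. The power claim is unaffected. Because the defect lies in the decision rule for the primary claim, it must be corrected.

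**What to change.** In section 9.2, state the prior for each arm, say that the interim threshold applies at each of the three interims, and recalibrate to the four looks. Two sets work on the 40/80/120/160 schedule. Power and expected N are at 25% versus 15% with uniform priors.

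| Interim / final | Max type I error, uniform | Max type I error, Jeffreys | Power | Expected N |
|---|---|---|---|---|
| 98% / 96% (current) | 6.8% | 7.5% | 95.6% | 172 |
| 99.5% / 96% | 4.7% | 4.8% | 95.0% | 217 |
| 99% / 97% | 4.5% | 5.0% | 93.9% | 196 |

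With 36/72/108/144 per arm, Jeffreys priors and a 10% CTC yield, the two options reach 5.11% and 5.23%. The chosen thresholds should therefore be confirmed by simulation over a grid of CTC yields with the stated prior, and the achieved error reported in 9.1. Power with 10% attrition and uniform priors is 93.0% and 91.5%. Carry the revised thresholds over to superiority and include that test in the same simulation; the figures here cover non-inferiority only.

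If the sponsor keeps 98%/96%, section 9.1 should instead state a level of about 7% one-sided, adjusted to the prior chosen.

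The cost is protocol and SAP wording, one simulation run and somewhat later early stopping. The 320 maximum is unchanged.
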